5.0 FREQUENTLY USED ABBREVIATIONS AND ACRONYMS

ACD	Allergic Contact Dermatitis
AE	Adverse Event
BLA	Biologics License Application
CRF	Case Report Form
FDA	Food and Drug Administration
GCP	Good Clinical Practice
HPC	Hydroxypropyl cellulose
ICH	International Conference on Harmonization of Technical Requirements for Registration of Pharmaceuticals for Human use
ICDRG	International Contact Dermatitis Research Group
IEC	International Ethics Committee
IR	Irritant Reaction
IRB	Institutional Review Board
MPA	Medical Products Agency
PVP	Polyvinylpyrrolidone, povidone, polyvidone (PVP)
SAE	Serious Adverse Event
SOP	Standard Operating Procedure
T.R.U.E. Test	Thin-Layer Rapid Use Epicutaneous Test
UV	Ultraviolet

6.0 BACKGROUND AND RATIONALE

6.1 Metal Allergy

As a group, metals are the most common contact allergens. Contact allergy to metals such as nickel, cobalt, and chromium is prevalent in the general population. It is estimated that up to 17% of women and 3% of men are nickel allergic, and that about 1 to 2% are allergic to cobalt, chromium, or both. Metal-induced allergic contact dermatitis (ACD) is expressed in a wide range of cutaneous reactions following prolonged or repeated exposure to personal products such as cosmetics, tattoos, detergents, jewelry, piercing studs, leather goods, cell phones, clothing buttons, snaps, zippers, partial dentures, dental braces and restorations. Occupational exposure in the metal and construction industries is also a significant risk factor for metal allergy reports. Apart from the well-known significance of nickel, cobalt, chromium and gold in developing ACD, other metals such as aluminum, beryllium, copper, iridium, indium, mercury, palladium, platinum, rhodium, molybdenum, manganese, zinc, cadmium and titanium have been reported as increasing causes of skin hypersensitivity.

6.2 Aluminum

The use of aluminum exceeds that of all other metals, except iron, and is used in all segments of the world's economy. It weighs about one-third as much as steel or copper; is malleable, ductile,

and easily machined and cast; and has excellent corrosion resistance and durability. Some of the many uses for aluminum are in transportation (automobiles, airplanes, trucks, railcars, marine vessels, etc.), packaging (cans, foil, etc.), construction (windows, doors, siding, etc.), consumer durables (appliances, cooking utensils, etc.), electrical transmission lines and machinery.

Aluminum compounds have a wide range of uses in industrial, domestic, consumer and medicinal products. The following summarizes several uses (3):

- Aluminum alkoxides- varnish, cosmetics and pharmaceuticals
- Aluminum borate- glass and ceramics
- Aluminum carbonate- antacids
- Aluminum chloride- (anhydrous) rubber, lubricants and antiperspirants
- Aluminum chloride- (hexahydrate) deodorants, antiperspirants, cosmetics and astringents
- Aluminum hydroxide- stomach antacids, antiperspirants, dentifrices and cosmetics
- Aluminum isopropoxide- soap and paint
- Aluminum nitrate- antiperspirants
- Aluminum phosphate- stomach antacids
- Aluminum silicate- dental cement, antacids and food additives

Typical causes of sensitization to aluminum are injections and vaccines. Aluminum compounds have been widely used as adjuvants in prophylactic and therapeutic vaccines as they prolong the period of absorption and increase the immune response. The two main clinical features of aluminum sensitization are persistent granulomas and recurrent eczema. Aluminum allergies seem to be more common in pediatric patients than adults. Children with aluminum sensitivity have been reported to develop subcutaneous nodules at the sites of injection or excoriated papules at the sites of hyposensitization therapy.

Prolonged use of antiperspirant and topical medications containing aluminum may also cause sensitization to aluminum. Clinical manifestations of aluminum sensitization are axillary rashes and hand dermatitis.

Pruritus due to allergic conditions has been seen after use of toothpaste containing 30-40% of aluminum oxide.

Researchers have proposed that tattoo pigments containing aluminum can induce granulomatous reactions. In 87% of tattoo ink studies, the most commonly identified element was aluminum.

6.3 Copper

Copper is a ductile metal with very high thermal and electrical conductivity. It is used as a conductor of heat and electricity, a building material, and a constituent of various metal alloys.

The major applications of copper are in electrical wires (60%), roofing and plumbing (20%) and industrial machinery (15%). Copper is mostly used as a pure metal, but when a higher hardness is required it is combined with other elements to make an alloy (5% of total use) such as brass and bronze.

Numerous copper alloys exist, many with important uses. Brass is an alloy of copper and zinc. Bronze usually refers to copper-tin alloys, but can refer to any alloy of copper such as aluminum bronze. Copper is one of the most important constituents of carat silver and gold alloys and carat solders used in the jewelry industry and the alloy of copper and nickel, is used in low-denomination coins. Copper is used in dental alloys and in intrauterine devices. Copper is also used in wood preservatives, antimicrobial textile treatments, ceramic glazes, stained glass, musical instruments and electroplating. Copper is also found naturally in foods but may also be introduced during preparation.

6.4 Manganese

Manganese is a chemical element found as a free element in nature (often in combination with iron), and in many minerals. Manganese is a metal with important industrial metal alloy uses, particularly in stainless steels. It is used as a treatment for rust and corrosion prevention on steel and as industrial pigments. Manganese dioxide is used as the cathode (electron acceptor) material in zinc-carbon and alkaline batteries. The second large application for manganese is as alloying agent for aluminum. Corrosion-resistant aluminum/manganese alloys are used for most beverage cans. Manganese compounds have been used as pigments and for the coloring of ceramics, glass and some paints and as a reagent in organic chemistry. Manganese chloride is used in oral agents for an MRI of the abdomen and/or pelvis. Manganese oxide is used in plant food.

6.5 Molybdenum

Molybdenum, a chemical element, occurs in various oxidation states in minerals. The majority of molybdenum produced is used in metallurgical applications such as structural steel, stainless steel, tool & high-speed steels, cast iron, molybdenum elemental metal, and super alloys, with the remaining portion used as compounds in chemical applications. The ability of molybdenum to withstand extreme temperatures without significantly expanding or softening makes it useful in applications that involve intense heat, including the manufacture of armor, aircraft parts, electrical contacts, pigments, catalysts, industrial motors, and filaments. Molybdenum is also used as a fertilizer for some plants, as a solid lubricant, a high-pressure high-temperature anti-wear agent, an adhesive between [enamels](#) and metals, a coloring agent in ceramics and plastics as well as in biological staining procedures.

6.6 Tin

Tin is a silvery, malleable poor metal used to coat other metals to prevent corrosion. Tin is used in many alloys, most notably tin/lead soft solders, tin plating, tin chemicals, brass and bronze, solder and niche uses.

Tin is most commonly alloyed with copper and may be found in some coins. Tin is also found in some dental amalgams and fluoride treatments.

6.7 Titanium

Titanium (IV) oxide is used as pigment to color paints, sunscreens, cosmetics, skin care products, plastics, papers, inks, medicines, toothpastes, and foods such as milk. It is also a thickener found in tattoo pigment and styptic pencils. It has UV resistant properties and is therefore used to act as a UV absorber.

6.8 Vanadium

Vanadium is a hard, silvery gray, ductile and malleable transition metal used in applications for bicycle frames, cranks, axles, and gears. It is also found in orthopedic and dental implants, glass coatings and jewelry. It is mainly used to produce specialty steel alloys such as high speed tool steels. The most important industrial vanadium compound, vanadium pentoxide, is used as a catalyst for the production of sulfuric acid. Various vanadium oxides are also used in making ceramics, glass coatings and jewelry.

6.9 Zinc

Zinc is a metallic chemical element used in the manufacture of cement, paper and textile processing it is an accelerator in the production of rubber. It is found as a pigment in paint and as a primer for galvanized iron and other metal substrates. Other applications include batteries, small non-structural castings, and alloys, such as brass (copper and zinc). A variety of zinc compounds are commonly used, such as zinc carbonate and zinc gluconate (as dietary supplements), zinc chloride (in deodorants), zinc pyrithione (antibacterial agent, anti-dandruff shampoos), zinc sulfide (in luminescent paints), and zinc methyl or zinc diethyl in the organic laboratory.

[figure not shown]
6.10 Patch Testing with Metals

A broad array of metals is available for patch testing today. These allergens are manufactured in a petrolatum, aqueous or alcohol based excipient and sold in syringes throughout the world although none have been submitted to the FDA or to the MPA in conformance with the Biologics License Application (BLA) or Medicinal Product Application procedures.

6.11 T.R.U.E. TEST®

T.R.U.E. TEST®, (Thin-layer Rapid Use Epicutaneous Patch Test) was originally granted a Biologics License for 23 allergens and a blank patch (control) in 1994 (BL No. 1623). The allergens were selected from substances widely reported to induce Allergic Contact Dermatitis (ACD). As new allergens become clinically relevant in the U.S. population, there is an ever-growing need to expand the number of allergens included in T.R.U.E. TEST®. The next 5 allergens were added to a third panel of the T.R.U.E. TEST® product in 2007 (BL103738/5019 and BL 103738/5027). An additional seven allergens were added in 2012. The current U.S. available T.R.U.E. TEST® product includes three panels of 36 allergen polyester patches including a blank patch (control). Each 0.81 cm² allergen patch is coated with one specific allergen or allergen mix. The allergens/allergen mixes are incorporated in exact dosage in a hydrophilic gel. The allergen-gel preparation is coated on an impermeable backing of polyester and dried to a thin film. The coated sheet is then cut into 9 mm x 9 mm squares (test patches), which are mounted on tape forming a standard test panel. The 3 panels together form a standard test kit. All 3 panels are typically applied to the skin of the upper back. The humidity of the skin hydrates the film and transforms to a gel, allowing the allergen to migrate into the skin, thereby reaching the cells of the immune system. The test is removed after 48 hours and read at 72-96 hours after the application, when the allergic responses are fully developed and mild irritant reactions have faded. Additional readings at 1 week and 21 days after panel placement are also advised in some cases.

Figure 1: T.R.U.E. TEST® Panel

6.12 Metal Panel T.R.U.E. TEST

Today the T.R.U.E. TEST® contains the only patch test allergens that have been submitted to the FDA and approved for sale in the United States. As such, these allergens require extensive developmental and clinical trial work prior to submission for approval. The clinical trials require subjects with suspicion of contact allergy (possibly to metals) or local inflammation potentially associated with a metal implant to determine both the appropriate dose for the allergen as well as the safety & efficacy of the proposed product.

Because metal contact allergy is increasing there is a need to develop a series of standardized metal patch test allergens utilizing the same allergen delivery technology as used in the T.R.U.E. TEST® product. Metal Panel T.R.U.E. TEST will be indicated for patients exposed to cardiac implants (stent, pacemaker, etc.), orthopedic implants (knee, hip or other), gynecological implants or devices, surgical hardware (plates, screws, wires, pins, rods, expanders, staples), dental metal implants, or dental metal appliances, prostheses or fillings whose exposure to has resulted in:

- Inflammation associated with an oral metal implant:
 - Burning mouth syndrome
 - Oral lichen planus
 - Oral lichenoid lesion
 - Palmo plantar pustulosis
 - Stomatitis: gingivitis, cheilitis and/or glossitis
- Itching, papules or nodules at injection site of aluminum containing vaccination
- Dermatitis over site of metal implant
- Systemic contact dermatitis
- Accelerated restenosis of cardiac stent
- Aseptic loosening
- Persistent joint pain

Other symptoms may also be associated:

- Persistent and recalcitrant dermatitis
- Dorsal or patchy hand dermatitis
- Leg and foot dermatitis
- Facial dermatitis (excluding seborrheic)
- Discoid dermatitis
- Dermatitis with unusual distribution
- Atypical allergic symptoms

In addition to the 8 metals on this study, is anticipated that Metal Panel T.R.U.E. Test will include metals currently available on T.R.U.E. TEST® and additional metals being investigated in a separate protocol.

- Nickel sulfate (currently on T.R.U.E. TEST®)

- Potassium dichromate (currently on T.R.U.E. TEST®)
- Cobalt dichloride (currently on T.R.U.E. TEST®)
- Gold sodium thiosulfate (currently on T.R.U.E. TEST®)
- Ammoniated Mercury (investigated in separate protocol)
- Sodium tetrachloropalladate (investigated in separate protocol)

The four common allergens (nickel, chromate, cobalt and gold) have been added to this protocol for diagnostic purposes only. Subjects with a strong suspicion of metal contact allergy should be tested with the most common metal allergens in addition to the 8 experimental (dilution series) metal allergens in order to give them a complete diagnosis. The common allergens will be tested as approved for T.R.U.E. Test but are considered experimental for this study due to reconfiguration of allergen placement on the test panel. Positive results from the common allergen testing will be tabulated in the final report only. No additional analysis will be performed using this data.

7.0 OBJECTIVE

To evaluate the diagnostic performance and safety of metal allergens proposed for inclusion in Metal Panel T.R.U.E. Test. The study will compare the diagnostic performance (primary) and safety (secondary) of ascending patch test doses of aluminum, copper, manganese, molybdenum, tin, titanium, vanadium and zinc allergens.

To determine if subjects who have not had previous patch testing are allergic to any of the most common metal allergens; nickel, cobalt chromium and gold.

7.1 Primary Endpoint

Determination of optimal test allergen dose as:

- The lowest concentration of each dilution series allergen eliciting positive responses in a minimum of 15 subjects. Positive responses are defined as score of 1+, 2+ or 3+ during at least one reaction assessment visit. If a significant number of 3+ responses are elicited, the dose will be selected based on 1+ and 2+ responses.
- For all sites with the exception of Germany: Concordance will be measured using Cohen's kappa where less than 0% indicates no agreement, 0-20% indicates poor agreement, 20-40% indicates fair agreement, 40-60% indicates moderate agreement, 60-80% indicates good agreement and 80% or higher indicates very good agreement. Concordance will be measured using all subjects who are tested with each allergen and corresponding reference allergen.

7.2 Secondary Endpoint

Determination of allergen safety

- Frequency of tape and polyester chip induced irritation or allergic reactions at Visits 2 through 6.

- Frequency of subject reported sensations of itching and/or burning for each allergen panel at patch removal.
- Frequency of positive (1+, 2+, 3+) skin reactions for each investigational and reference allergen dose at each post removal visit and overall.
- Frequency of negative, doubtful, irritant, late and persistent skin reactions for each investigational and reference allergen dose at each post removal visit (late and persistent reactions at visits 4, 5 and 6 only).
- Frequency of all adverse events. Documentation for all local and systemic adverse reactions classified by the investigator as possibly or definitely related to the study product (e.g., erythema, hyper-pigmentation, hypo-pigmentation, skin thinning or dermatitis flare) will include grade (mild, moderate or severe) and time point (clinic visit).

8.0 STUDY DESIGN

8.1 Overview

This is a prospective, multi-center, randomized, double-blind design. That is, the allergen doses on each panel will be randomized into three different configurations, which will be randomly assigned to subjects as they enter the study. Although the investigators and subjects will know which allergen is being tested, they will be blinded to the placement of the allergen doses within each panel. A 48-hour application (approximate) of investigational allergen panel(s), an excipient control and corresponding reference petrolatum (or aqueous) allergen(s) will be applied to the skin of human subjects to test for potential positive allergic responses. Test sites will be evaluated at 3-4, 7-8, 10-14 and 19-23 days after application. The chosen evaluation times are consistent with generally accepted international patch test guidelines and are designed to prevent missed late reactions and false negatives. The final clinic visit (day 21) allows the investigator to evaluate any late or persistent localized reactions. The investigator may choose to perform this visit via telephone if there are no residual reactions. If there are persistent escalating reactions noted at Visit 6, the investigator will determine and record follow up action.

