If yes, list current symptoms: _____

Suspicion of contact allergy associated with metal exposure

Type of metal exposure

- Cardiac implant (stent, pacemaker, etc.)
- Orthopedic implant (knee, hip or other)
- Gynecological implant or device
- Surgical hardware (plates, screws, wires, pins, rods, expanders, staples)
- Dental metal implant
- Dental metal appliance, prosthesis or filling
- Injection of aluminum containing vaccination
- Other _____

Other reason Investigator believes the subject qualifies for study inclusion

Past positive lymphocyte proliferation (or transformation) test to one of the dilution series metals being tested on this study

Name of metal tested: _____

Date of test: _____

Results: _____

Other _____

Figure 4: Type of Metal Exposure Questionnaire

Name of Procedure	_____	
Date of Procedure	_____	
Date symptoms first began	_____	
Patient's description of symptoms	_____	
Site(s) of onset	_____	
Symptoms currently present?	 Yes	 No
Duration	 Continuous	 Sporadic
If sporadic:	_____	
How long do symptoms last?	_____	
What is the length of time between episodes?	_____	
Other symptoms? (itching, burning, pain, etc.)	_____	
Medication Taken?	 Yes	 No
If yes:	_____	
Name of Medication	_____	
Start Date	_____	
Stop date (or ongoing)	_____	
Dose	_____	
Frequency	_____	
Route	_____	

Subjects who qualify for participation will have the investigational allergen panel(s) and reference allergens applied (with the exception of subjects enrolled in Germany who will not be tested with the reference allergens) to the paraspinal region of the upper back. Areas of contact dermatitis, uneven skin tones, tattoos, scars, moles, excessive hair or other skin disfigurement should be avoided. Upper arms may be used if there is not adequate space on the back for all panels. In summary, within these parameters, investigators will use their medical expertise to determine panel placement based on the features of each subject's back as they would normally do in clinical practice.

Panels may be further secured with medical tape (e.g., Scanpor® or patchProtect™). PatchMap may be used to document panel placement. The use of PatchMap will be required in Germany. The time of application will be documented.

The panel will be applied to the subject populations per the following:

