 - Panel 6: Chips on positions 1-4 and 7-9 will be evaluated for irritation. If Panel 6 is cut to avoid patch testing with the common allergens chips on the remaining positions will be evaluated.
- Panels 7-8: Irritation attributed to the adhesive used to adhere the panels to the skin (tape irritation) will be documented if the site of the entire panel with the exception of the patch test chambers show signs of irritation. This will be similar to the tape irritation example shown below in Figure 5 but the chambers used in the Finn Chamber product are round, not square.

Figure 5: Tape vs Chip Irritation Illustration

Tape Irritation:

Site of entire panel *with exception of chip sites* shows signs of skin irritation

Chip Irritation:

Only chip sites show signs of irritation.

NOTE: *All sites* must have the same or nearly the same degree of irritation.

Position 1  Position 7 

Position 2  Position 8 

Position 3  Position 9 

Position 4  Position 10 

Position 5  Position 11 

Position 6  Position 12 

Tape irritation will be evaluated according to the following score scale:

None: No erythema or other sign of irritation

Weak: Faint to definite pink erythema

Moderate: Moderate erythema, definite redness

Strong: Severe erythema, very intense redness

Polyester chip induced irritation will be evaluated according to the following score scale:

None: No erythema or other signs of irritation

Weak: Faint to definite pink erythema at **all** polyester chip sites*

Moderate: Moderate erythema, definite redness at **all** polyester chip sites*

Strong: Severe erythema, very intense redness at **all** polyester chip sites*

*To ensure that irritation resulting from skin contact with the polyester chip is not confused with an allergic response to a specific allergen, all of the polyester chip sites on each panel must present the same or nearly the same degree of irritation.

Subject self-report of itching and burning sensations for each allergen panel will be documented according to the following score scale:

None: No discomfort
Weak: Minimal discomfort
Moderate: Definite discomfort
Strong: Significantly bothersome; possible interference with sleep or daily activity

Subject-reported adverse events, worsening of a pre-existing condition/disease/symptom or changes to concomitant medications will be recorded.

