2. Categorize the skin reactions at each site as either negative or positive. No skin reaction scores (1+, 2+ or 3+) assigned to during any of the reaction assessment visits, (Visits 3-6) would constitute a negative reaction. A positive skin reaction is defined as an assigned score of 1+, +2 or 3+ during at least one of the reaction assessment visits (Visits 3-6).

[figure not shown]

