The lead chemist in the department of pharmaceutical development at SmartPractice Denmark is responsible for the randomization of allergens on panels 1-5. The allergens will be randomized within each panel into three different configurations, per standard protocol. The different allergen configurations will be randomly assigned to subjects as they enter the study. The investigators and subjects will be aware of the allergens and the patch test doses on the test panels but will not be aware of the placement of the allergens on the individual panels (the different panel configurations). The key to the randomization scheme will be kept confidential at SmartPractice Denmark until it is forwarded to data management for analysis of the study results following completion of all study related procedures.

The allergens on panel 6 will not be randomized into different configurations. Should the Investigator elect to omit the common allergens from an individual's patch testing, the panel should be cut as shown below in Figure 9.

Figure 9: Panel 6 Configuration and Cutting Instructions

Unused portion of the panel is not to be discarded.

The remaining portion of the panel must be applied as it contains the excipient and blank patch controls. Scores for the blank (Position 4), PVP (Position 8), and HPC (Position 9) patches will be recorded in the case report forms as originally intended, in fields for positions 4, 8 and 9. Positions 1, 2, 3 and 7 will be documented in the case report form as 'not applied'.

All investigational products used in this study must be accounted for. Records must show amount and date of delivery of all test materials to the investigator. Likewise dates, amount, and signatures should document return of unused test panels. Product deliberately and/or accidentally destroyed by the investigator must also be documented.

The use of the investigational product for the individual subject, including number and identification of specific panels applied, application (or not) of common allergens and date and time of application and removal will be documented.

The following investigational panels with ascending doses of allergen and an excipient control will be used in this study.

Panel 1 Aluminum Dilution Series

Allergen	Excipients	Ascending Dosages (mg salt/cm ²)	Randomized Among Positions
Aluminum chloride hexahydrate	Water, Ethanol (99.9%), PVP	0.040, 0.12, 0.36, 0.72	1-4 and 7-10

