11.2 Reference Allergens

Commercially available reference allergens may be used or the reference allergen syringes may be prepared and labeled by the Department of Occupational and Environmental Dermatology, Skåne University Hospital, Malmö, Sweden. The reference allergens will be stored in individual syringes under refrigeration at 2 - 8°C.

The Finn Chamber, polypropylene-coated, supplied by SmartPractice, will be used to apply the reference allergens. Reference allergens will be dispensed at the rate of 20 µl/chamber using a precision allergen dispenser.

Figure 10: Reference Allergen Preparation

Petrolatum allergens

◀ Apply a ribbon of substance across the diagonal of chamber

Petrolatum allergens may be dispensed 24 hours prior to application

Liquid allergens

◀ Add filter paper to chamber

Dispense liquid allergen to chamber ➔

Liquid allergens may not be dispensed until immediately prior to patch application

Instructions for precision allergen dispenser:

1. Fill metering chamber with allergen using syringe plunger.
2. Wipe excess from tip.
3. Dispense allergen to chamber by depressing precision allergen dispenser plunger.

- The Aluminum Dilution Series will be tested concurrently with
 - Aluminum chloride hexahydrate, 10 % w/w in petrolatum
 - Aluminum lactate, 12 % w/w in petrolatum
- The Copper Dilution Series will be tested concurrently with copper sulfate anhydrous, 2 % w/w in petrolatum
- The Manganese Dilution Series will be tested concurrently with manganese chloride tetrahydrate, 2 % w/w in petrolatum
- The Molybdenum Dilution Series will be tested concurrently with ammonium molybdate, 1% aqueous solution.
- The Tin Dilution Series will be tested concurrently with tin chloride dihydrate, 1% w/w in petrolatum
- The Titanium Dilution Series will be tested concurrently with
 - Ammonium titanium peroxy citrate, 17% w/w in petrolatum
 - Ammonium titanium lactate, 34% aqueous solution
 - Potassium titanium oxide oxalate, 22% w/w in petrolatum
 - Ammonium Titanium oxide oxalate 19% w/w in petrolatum
- The Vanadium Dilution Series will be tested concurrently with
 - Vanadium chloride, 1% w/w in petrolatum
 - Vanadium oxide sulfate, 1.5% w/w in petrolatum
- The Zinc Dilution Series will be tested concurrently with zinc chloride, 2% w/w in petrolatum

NOTES: 1) The common allergens (Panel 6) will not be tested against reference allergens. 2) Subjects enrolled in Germany will not be tested with the reference allergens

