Overall concordance of skin reaction responses from each allergen dose will be compared with reference allergen by using Kappa statistic as described below,

Kappa statistics (K) = $(P_0 - P_e) / (1 - P_e)$

Where P_0 is the relative observed agreement among raters (identical to accuracy), and P_e is the hypothetical probability of chance agreement and the Kappa agreement statistics score is interpreted as,

≤ 0 as indicating no agreement

0.01 – 0.20 as poor agreement

0.21 – 0.40 as fair agreement

0.41 – 0.60 as moderate agreement

0.61 – 0.80 as good agreement

0.81 – 1.00: very good agreement

Concordance will be measured using all subjects who are tested with each allergen and corresponding reference allergen.

Note: Data from the subjects with the completely detached patches for the intended wear period (approximately 48 hours or two days) will not be included in the analysis of positive responses necessary to determine optimal dose.

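### The reference patches lie outside the blind and no reading order is set, so the test and reference readings compared by kappa may not be independent

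*Protocol*

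**What the plan says.** **Scope of the blind.** Protocol 4.7 and 8.1 and SAP 3.1 call the study double-blind and then define the term. Investigators and subjects know which allergen is tested, but "they will be blinded to the placement of the allergen doses within each panel". Protocol 11.1 adds: "The investigators and subjects will be aware of the allergens and the patch test doses on the test panels". The sponsor's lead chemist "is responsible for the randomization of allergens on panels 1-5", and the key stays confidential until study procedures are complete. The reference patches are not part of this.

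**Reference patches.** Under Protocol 11.2 they are dispensed from individual syringes into Finn Chambers, and "Petrolatum allergens may be dispensed 24 hours prior to application". Protocol 10.2 treats the reference patches as Panels 7-8 and notes that "the chambers used in the Finn Chamber product are round, not square". No coding, concealed order or masked reading is described. Protocol 10.1 has both patch types applied at Visit 1: "Subjects who qualify for participation will have the investigational allergen panel(s) and reference allergens applied" to the upper back, or the upper arms if space is short. Subjects in Germany receive no references.

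**Positions.** The panel tables in Protocol 11.1 fix the positions of each metal on Panels 2 and 3. On Panels 1, 4 and 5 the salts and doses are randomized together across all positions used.

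**What enters kappa.** After Visit 6 the Investigator is to "Categorize the skin reactions at each site as either negative or positive" (Protocol 10.6). A site is positive if it scored 1+ or more at any of Visits 3-6. SAP 6.1 takes the Investigator Determination of both patch types and computes kappa for each dose against the reference, as the second part of the primary endpoint.

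**The concern.** Concealing dose position protects comparisons between doses: a reader cannot favour a dose whose location is unknown. It does not protect the comparison of test with reference, which is the one kappa reports. A reader who sees a clear reaction at a reference chamber may score a faint reaction at the matching test chips differently, and the same can happen in the other direction.

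The scoring leaves room for this. At Visit 3 the boundary between doubtful and 1+ is non-palpable against palpable erythema (Protocol 10.3.2). At Visits 4-6 the listed scores are only negative, 1+, 2+ and 3+ (10.4.2, 10.5), so a faint site must go one way or the other. A single 1+ at any reading visit makes the site positive.

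The agreement grade reported for each dose is at stake. So, less directly, is the number of positives counted toward the 15-subject rule. German subjects have no references, so the pooled dose counts would also mix readings made with and without this cue.

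**Working it through.** **1. How far the existing blind reaches (panel tables, Protocol 11.1).**

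| Panel | Series | Chips | Metal known by position? |
|---|---|---|---|
| 1 aluminum | 2 | 8 | One metal; salt hidden |
| 2 copper, zinc, tin | 3 | 12 | Yes: copper 1, 2, 7, 8; zinc 3, 4, 9, 10; tin 5, 6, 11, 12 |
| 3 manganese, molybdenum | 2 | 8 | Yes: manganese 1-4; molybdenum 7-10 |
| 4 titanium | 4 | 12 | One metal; salt hidden |
| 5 vanadium | 2 | 8 | One metal; salt hidden |

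In total there are 13 series and 48 chips. A reference can be matched to its own four chips in 3 + 2 = 5 series (12 + 8 = 20 chips). In the other 2 + 4 + 2 = 8 series (8 + 12 + 8 = 28 chips) the salt is hidden, and only a general pull by metal is possible. The dose is hidden in all 13.

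**2. Illustration with the SAP formula.** Kappa = (P0 − Pe)/(1 − Pe). The plan gives no expected kappa, positivity rate or degree of reader influence, so the counts below are assumptions. They are subject-level determinations, listed as both positive, reference only, dose only, neither.

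- Independent readings (9, 9, 6, 276): P0 = 285/300 = 0.950. Pe = (18×15 + 282×285)/300² = 0.896. Kappa = 0.054/0.104 = 0.519, moderate. The large-sample 95% interval is about 0.31 to 0.73.
- Three reference-only subjects become both positive and two dose-only subjects become neither (12, 6, 4, 278): P0 = 290/300 = 0.9667. Pe = (18×16 + 282×284)/300² = 0.8931. Kappa = 0.0736/0.1069 = 0.688, good.

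Five of the 15 discordant determinations moved. Positives at the dose go from 9 + 6 = 15 to 12 + 4 = 16, so the 15-subject rule is met either way.

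**3. Range.** Take 400 subjects. A share q of discordant pairs is read into agreement, half to both positive and half to both negative.

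| Positive on either patch; share positive on both | q = 0 | 10% | 20% | 30% |
|---|---|---|---|---|
| 30; one third | 0.47 | 0.53 | 0.58 | 0.63 |
| 30; one fifth | 0.30 | 0.37 | 0.44 | 0.51 |

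With 15, 30 or 60 subjects positive on either patch and 20-50% of them positive on both, q of 10-30% raises kappa by about 0.03 to 0.22. With no true association, kappa is about equal to q instead of 0.

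**4. Dose counts.** Assume 30 of 400 are reference-positive. Across four rising doses, 6, 12, 18 and 22 are positive on both patches, and 1, 2, 4 and 8 on the dose only. Positives per dose are then 7, 14, 22 and 30. If 10% of discordant test readings move toward the reference, the second dose goes from 14 to 12 + 0.1×18 + 0.9×2 = 15.6, past 15. The example starts just below the threshold, so it shows what is possible and does not estimate an effect.

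**The case against.** Much of the case on the other side stands.

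- **One reader with both sites in view.** A reader might infer that one person scores both patch types side by side. The documents name the Investigator as a role and provide no second reader, but they do not say that one individual reads both. Placement is left to the investigator, so adjacency is not established either.
- **A false claim of blinding.** The documents do not make one. They define the blind as dose placement and say that the allergens are known. The gap is that nothing is said about the references.
- **The SAP wording on raters.** SAP 6.1 says that P0 "is the relative observed agreement among raters". One might read this as a commitment to two readers. It is ordinary formula wording; kappa here compares two patch methods within a subject.
- **Protection from hidden positions.** Direct matching is possible for 5 of 13 series, and the dose stays hidden even there.
- **Size.** The shift from 0.52 to 0.69 assumes that a third of all disagreement moves, entirely toward agreement, and it lies inside the sampling interval of the starting value. Because any 1+ at Visits 3-6 counts, one reading scored down does not make a site negative. The illustration therefore holds for final determinations, not for single readings.
- **Consequence.** Protocol 7.1 and SAP 4.1 attach labels to kappa but no pass mark.

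What remains is that nothing in the plan protects the test-to-reference comparison from expectation. A sampling interval does not reflect a systematic shift, and a larger sample would not remove one.

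**Conclusion.** The point holds as a limitation with a cheap remedy. The blind covers dose placement on Panels 1-5. The references have no concealed order, set reading order or separate reader, and for five of 13 series a reader can match a reference reaction to its test chips. The two determinations entering kappa may therefore not be independent, and agreement could be overstated.

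The upward direction is plausible but not proven, and the documents do not give its size. The kappa figures above rest on assumed counts and assumed reader influence. The documents do not support saying that kappa will be inflated or that the selected dose will be wrong. With no pass mark, the main effect is on the agreement label and its interpretation. An effect on dose selection is possible only where the number of positives lies close to 15.

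**What to change.** 1. **Reading order (Protocol 10.3.2, 10.4.2, 10.5).** At each in-person reading, cover the Panel 7-8 sites, score and lock Panels 1-6, then uncover and score Panels 7-8. Put the CRF pages in that order.
2. **Reference order (Protocol 11.2).** Where existing staff other than the reader load the chambers, use one of several preset reference orders and release the key after Visit 6. This helps only subjects who receive more than one reference.
3. **Description of the blind (Protocol 4.7, 8.1; SAP 3.1).** State that the reference allergens are not blinded or, where preset orders are used, that their order is concealed.
4. **Interpretation (SAP 6.1).** State that kappa compares two patch methods whose readings may not be independent.

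The cost is a cover, a change of CRF page order and a minute or two per visit, with no extra reader. Masking remains partial. Locking first keeps the reference cue out of the test scores at that visit, but test scores can still influence the reference scores that follow. Earlier scores may be recalled at Visits 4-6, and the Panel 7-8 sites are already inspected for tape irritation at Visit 2. If the readings are already complete, items 3 and 4 still apply, with the description stating what was done.
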